The objectives of this pilot randomized controlled trial are to (1) determine the feasibility and acceptability of study procedures (recruitment, randomization, and data and sample collection) and CSM-IBD; (2) compare CSM-IBD to usual care on changes from baseline to 3 months post intervention in quality of life and daily symptoms (fatigue, sleep disturbance, psychological distress, gastrointestinal symptoms) among IBD patients and (3) explore the association of socioecological factors (age, sex, race, ethnicity, or diet), clinical phenotype (medications, disease distribution, and disease activity), and biological signatures (microbiome and calprotectin) with symptoms at baseline and response to intervention (post intervention).

Methods

Study Design

The proposed study is a 2-arm pilot randomized controlled trial that follows the Consolidated Standards of Reporting Trials and Standard Protocol Items: Recommendations for Interventional Trials guidelines [30,31]. In a 2:1 ratio, 54 participants will be randomized (intervention=36 participants; usual care=18 participants). This randomization scheme was selected to maximize data collection and information regarding the intervention group. The intervention will take place over 8 sessions. The participants will be blinded to the study hypotheses. Web-based self-reported questionnaires will be used to reduce detection bias.

Theoretical Framework

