5. Intervention feasibility: measured with the Feasibility of Intervention Measure, in which participants respond to 4 questions on a 5-point Likert scale from 1=completely disagree to 5=completely agree at the end of the intervention [37].

Acceptability Outcomes

A semistructured interview guide will be used to assess the acceptability of study procedures as well as the acceptability and satisfaction with the CSM-IBD. For instance, questions will probe for clarity of instructions, the burden of study procedures, and satisfaction with intervention content and delivery. Transcripts from participant interviews will be coded by 2 individuals using open coding methods to evaluate intervention acceptability. The use of CSM-IBD strategies will be assessed at 3 months post intervention by asking participants how often they use each strategy, with response options as: not at all or rarely, occasionally (at least 1 day a week), often (at least 2 days a week), very often (at least 4 days a week), or almost always [38]. Participants will complete the Acceptability of Intervention Measure, which includes 4 questions rated on a 5-point Likert scale from 1=completely disagree to 5=completely agree [37]. Satisfaction will also be measured with the 8-item Client Satisfaction Questionnaire [39].

Primary Outcomes

Quality of Life

The SIBDQ is a 10-item questionnaire that evaluates the quality of life. Participants respond on a 7-item Likert scale from all the time to none of the time. Total score range: 10 to 70 [40].

Symptoms

Symptoms are measured using a numeric rating scale where participants report the severity of the symptom from 0=not present to 10=worst possible. Symptoms include abdominal pain, anxiety, bloating, constipation, depression, diarrhea, fatigue or tiredness, passing gas, sleepiness during the day, stress, and urgency.

Secondary Outcomes

1. Process variables [41,42]
 - Self-Efficacy for Managing Chronic Disease: a 6-item self-report scale. Participants report ranging from not at all confident to totally confident [21].
 - Index of Self-Regulation: a 9-item scale to measure an individual's level of self-regulation [43].
 - Patient Activation Measure: a 13-item scale that assesses patients' beliefs, knowledge, and confidence in managing their health [44,45].

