2. Biological signatures: stool samples will be collected by participants and stored immediately in home freezers (-20°C) before transport to the UW School of Nursing Biobehavioral Laboratory. Samples will be stored at -80°C until batch processing.
 - Gut microbiome: fecal microbial communities will be characterized using metagenomic shotgun sequencing on the Illumina MiniSeq or NextSeq platforms (Illumina, Inc) [46,47].
 - Fecal calprotectin: fecal calprotectin is a biomarker used to measure inflammation in the gut and will be assessed using an enzyme-linked immunosorbent assay [48].
3. Socioecological factors were selected based on the National Institute for Nursing Research's common data elements and include sex, gender, age, race or ethnicity, education level, employment, marital or partner status, household size, and neighborhood (urban or rural, zip code). Dietary intake can influence the composition of the gut microbiome and symptoms [49]. At the time of the stool collection, subjects will complete a detailed 3-day food record (Fred Hutchinson Cancer Research Center Nutrition Assessment).
4. The clinical phenotype will be obtained from the electronic medical record: type of disease, time since diagnosis, history of bowel surgery, disease distribution (measured by

the Montreal Classification), medications, and disease activity (Harvey Bradshaw Index for Crohn Disease [50] and Simple Colitis Activity Index for Ulcerative Colitis [51]; <5 indicates remission).

5. Health care use will be evaluated from the electronic medical record and patient self-report, including emergency department use, hospitalizations, outpatient visits, laboratory tests, imaging, and procedures, as well as providers' nonclinical time spent managing patients.

Participant Timeline

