Analyses of microbiome data will use 3 summary measures—Shannon diversity, richness, and *Firmicutes/Bacteroidetes* ratio—as well as the relative abundance of bacterial families (eg, family Ruminococcaceae) and genera and will control for the read count. For diet, we will focus on protein and fiber intake, as our previous work has indicated these may be important dietary intake components related to the gut microbiome. First, we will examine the associations between socioecological, clinical phenotype, and biological signatures with symptoms at baseline in the total sample using Pearson correlation or Spearman rank correlation based on measure distributions. Scatter plots will be used to visually display these associations. Second, we will examine associations between socioecological, clinical phenotypes, and biological signatures at baseline and response to intervention in the intervention group. Response to intervention is conceptualized as an increase of 8 points on the SIBDQ scale (quality of life) [40] or a 50% decrease from baseline in the GI symptom score [27]. Among the intervention group, we will use the *t* test and chi-square test to compare socioecological factors, clinical phenotypes, and biological signatures among patients with and without a response to treatment.

Monitoring

This study has been classified as a minimal-risk study. The principal investigator has the responsibility for study oversight, including patient safety and data quality, as well as submitting reports to the funder and the institutional review board. Due to the low-risk nature of the CSM-IBD, we do not anticipate any adverse events or serious adverse events. The data safety and monitoring team will meet quarterly to review the study. The team will monitor accrual, withdrawals, data quality, timeliness of data submission, protocol compliance, and the types and frequency of adverse events and serious adverse events. No interim analysis or stopping rules are currently planned. However, if any adverse events or serious adverse events are reported, the data safety and monitoring team will meet within a week to discuss the event and any potential changes needed to the study procedures.

Ethics and Dissemination

Data Management

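### Baseline aim 3 analysis: Pearson or Spearman correlation is the only method named, and neither suits a nominal factor entered with three or more unordered categories

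*Combined protocol and SAP*

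**What the plan says.** The Objectives section sets as its third aim to "explore the association of socioecological factors (age, sex, race, ethnicity, or diet), clinical phenotype (medications, disease distribution, and disease activity"), together with biological signatures, in relation to baseline symptoms and to response.

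Under Study Outcomes, Secondary Outcomes, item 3, the socioecological factors "include sex, gender, age, race or ethnicity, education level, employment, marital or partner status, household size, and neighborhood". Item 4 lists the clinical phenotype, including "type of disease, time since diagnosis, history of bowel surgery, disease distribution". Symptoms are 0 to 10 severity ratings (Primary Outcomes, Symptoms).

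The Secondary Outcomes paragraph of the Statistical Analysis section has two steps. The first relates all three groups of factors "with symptoms at baseline in the total sample using Pearson correlation or Spearman rank correlation based on measure distributions". The display is fixed as well: "Scatter plots will be used to visually display these associations". The second step, in the intervention group only, uses the *t* "test and chi-square test to compare socioecological factors, clinical phenotypes, and biological signatures among patients with and without a response to treatment". No levels, coding, collapsing rule or alternative method is given for nominal factors in the first step.

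**The concern.** Pearson correlation needs a numeric variable and Spearman needs at least an ordered one. Choosing between them by distribution does not help with a variable that has no order. Race or ethnicity, which objective 3 names, and employment and marital or partner status, which are on the collection list, have no natural order. If one of them is entered as codes 1, 2, 3 and so on, the coefficient measures a straight-line or monotone trend along an arbitrary sequence. Renumbering the same people changes its size and can reverse its sign.

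At stake is whether a difference in baseline symptoms between such categories would be found, and whether the reported coefficient would mean anything. The findings are meant to refine the intervention and shape a full-scale trial, so an uninterpretable coefficient for race or ethnicity would be an awkward input.

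**Working it through.** **The plan's own aim 3 figure.** The Sample Size section gives 80% power for a correlation of 0.45 and does not state the n. With Fisher's z and an assumed two-sided 5% level, power = Φ(atanh(0.45)·√(n−3) − 1.96).
- n=36: 0.4847 × 5.745 − 1.96 = 0.824, power 79.5%.
- n=54: 0.4847 × 7.141 − 1.96 = 1.501, power 93.3%.

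The figure matches the intervention arm rather than the total sample. It concerns a correlation between two measured variables and says nothing about nominal factors, so the present point does not depend on it.

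**Inputs for the check.** N=54 is from the plan. The category counts, category sizes, SD of 1, size of shift and two-sided 5% level are assumptions. One category is shifted by δ and the others are equal.

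**One-way ANOVA power.** The noncentrality is λ = n_s(1 − n_s/N)δ², where n_s is the size of the shifted category. Power is the probability that a noncentral F exceeds the 5% critical value, F(3,50)=2.790 for four categories and F(2,51)=3.179 for three.

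| Sizes, δ=1 | n_s | λ | ANOVA power | Pearson power, mean over code orders |
|---|---|---|---|---|
| 20/14/10/10 | 20 | 20×34/54 = 12.59 | 82.8% | 47.6% |
| 20/14/10/10 | 14 | 14×40/54 = 10.37 | 74.2% | 39.5% |
| 20/14/10/10 | 10 | 10×44/54 = 8.15 | 62.5% | 29.3% to 29.9% |
| 24/18/12 | 24 | 24×30/54 = 13.33 | 89.8% | 60.7% |
| 24/18/12 | 18 | 18×36/54 = 12.00 | 86.3% | 57.6% |
| 24/18/12 | 12 | 12×42/54 = 9.33 | 76.1% | 45.7% |

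The Pearson column comes from simulation, 10,000 data sets per scenario, over all 24 or 6 code orders. Single orders run from 4% to 82% (four categories) and from 4% to 90% (three). For four categories, Spearman averages 27% to 49% and Kruskal-Wallis reaches 57% to 80%.

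**Smaller shift, δ=0.5.** Four categories: ANOVA 18% to 27%, Pearson 11% to 19%. Three categories: ANOVA 25% to 34%, Pearson 17% to 26%.

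**Sparse case.** Sizes 30/12/8/4, the category of 4 shifted by 1 SD: ANOVA 31%, Pearson 12% on average.

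**One constructed data set.** Sizes 20/14/10/10, each category with SD exactly 1, the category of 14 exactly 1 SD higher. ANOVA: F = 10.37/3 = 3.457, p=0.023, whatever the coding. For Pearson, r = n_s(c_s − c̄)/√(Sxx·Syy), with c the codes and Syy = 50 + 10.37 = 60.37.
- Category of 14 coded 4, category of 20 coded 2, the two of 10 coded 1 and 3: c̄=2.519, Sxx=61.48, r = 14×1.481/√(61.48×60.37) = 0.340, p=0.012.
- Category of 14 coded 2, category of 20 coded 1, the two of 10 coded 3 and 4: c̄=2.185, Sxx=68.15, r = 14×(−0.185)/√(68.15×60.37) = −0.040, p=0.77.
- Reversing a code order reverses the sign, so r spans −0.340 to 0.340. In 12 of the 24 orders p<0.05.

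**Null.** With any single fixed code order and no true difference, Pearson rejects in 4.6% to 5.4% of data sets (four categories) and 5.0% to 5.1% (three).

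**Two categories.** Pearson gives the same p value as the equal-variance t test, so binary factors are handled correctly.

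**The case against.** The problem is conditional. The documents do not say at how many levels race or ethnicity, employment or marital status will be analysed; reduced to two levels, each suits Pearson. The paragraph is a short summary, and its t test and chi-square sentence, covering the same groups of factors, shows that the authors distinguish categorical from continuous measures. A reader might infer that the plan deliberately scores race as a number. The documents do not support that: they leave coding open. It still stands that the t test and chi-square sentence covers only responders against nonresponders in the intervention group, and that the baseline step, read as written, offers nothing else for a multi-category factor.

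The practical gain is also modest. The large contrasts need a full SD difference in one category, and an average over code orders describes no single analysis. At 0.5 SD, ANOVA still misses most four-category differences, and sparse categories stay weak under either method. The Sample Size section already says that only large differences or correlations can be detected. All of this is fair. It limits the power argument, but it does not rescue the meaning of a coefficient that changes with the numbering.

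Finally, the documents list no levels for disease distribution beyond naming a classification, so whether it is unordered cannot be settled from them.

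**Conclusion.** The point holds in a limited form. For race or ethnicity, employment, and marital or partner status, and for disease distribution only if its recorded levels are unordered, Pearson and Spearman do not suit a factor entered with three or more categories. In the illustrations at 1 SD, power falls from 63% to 83% under ANOVA to 29% to 48% on average under Pearson with four categories, and from 76% to 90% to 46% to 61% with three. These figures rest on assumed category counts, sizes and shifts; the dependence on code order does not.

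Three stronger conclusions are not supported:
- **More false positives.** A fixed code order keeps about 5% under the null. The harm is lost power and an uninterpretable estimate.
- **Wider damage.** The aim is exploratory. The treatment comparison and the feasibility outcomes are untouched.
- **A conflict over read count.** The plan says that microbiome analyses will cover summary measures "as well as the relative abundance of bacterial families (eg, family Ruminococcaceae) and genera and will control for the read count". A reader might infer that a two-variable correlation contradicts this. It need not: the control could be applied when the measures are prepared, or by partial correlation.

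**What to change.** Amend the baseline step in the Secondary Outcomes paragraph of the Statistical Analysis section as follows:
- Keep Pearson or Spearman for continuous, ordinal and binary factors.
- For nominal factors with more than two categories, compare symptom ratings by one-way ANOVA or Kruskal-Wallis, or by linear regression with indicator variables.
- State the categories, and any collapsing of sparse ones, before the outcome data are seen.
- For these factors, replace scatter plots with category means and confidence intervals, or box plots.

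The cost is one or two sentences and no new data. The downside is more degrees of freedom per factor. If the code order happened to match the true pattern, a single correlation would do about as well as ANOVA (82% against 83% at 1 SD) or slightly better (31% against 27% at 0.5 SD). Collapsing categories loses detail.

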Participants are individuals seeking care for their IBD at the University of Washington (UW). Inclusion criteria include participants who (1) have a health care provider diagnosis of IBD as reported in the electronic medical record, (2) report at least 2 current, active symptoms (Short Inflammatory Bowel Disease Questionnaire [SIBDQ] equal or less than 4 [“some of the time”] on any 2 items), (3) are 18 to 75 years old, and (4) are able to read and write in English.

Participant exclusion criteria include (1) pregnant individuals, (2) significant co-occurring mental or physical conditions that would impact study participation, (3) surgery or hospitalization within the past month, or (4) living outside of Washington State.

CSM Intervention

The 8-session CSM includes patient education about self-management of symptoms using CBT, relaxation training, and diet counseling. The intervention will be delivered digitally with skill videos, readings, and homework, as well as a weekly phone call or Zoom check-in with a nurse trained in CBT. For each session, participants will review information and practice skills on the session topic. The content for each session is outlined in [Table 2](#). The weekly phone calls are designed to provide accountability and support for achieving the session goals and to enable individuals to ask questions about the content. The estimated time of completion is 8 weeks; however, participants will have 12 weeks to complete the sessions to allow for unexpected events. Intervention fidelity will be monitored using fidelity checklists and through the evaluation of a random selection of 20% of participants.

Also of note, the original CSM intervention was administered as a paper workbook with weekly hour-long sessions with a trained advanced practice nurse. To improve accessibility and feasibility, we have adapted the intervention to be administered as a web-based intervention with weekly phone call check-ins with a CBT-trained nurse. This unique approach expands the feasibility and reach of the intervention by enabling patients who may live in rural or underserved areas to access the intervention content. To be appropriate for the IBD population, the session 1 disease content was modified to include the role of inflammation, the importance of endoscopic remission, and information on when to contact their health care provider. The intervention content was reviewed by patients and health care providers.

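### The responder rule for aim 3 accepts a 50% fall in an undefined GI symptom score with no minimum baseline, so response may partly reflect mild GI symptoms at entry

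*Combined protocol and SAP*

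**What the plan says.** Statistical Analysis, Secondary Outcomes, defines response to the intervention as a gain of 8 SIBDQ points "or a 50% decrease from baseline in the GI symptom score". Within the intervention group, t tests and chi-square tests then compare socioecological, clinical and biological factors between responders and non-responders.

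Three other places bear on this rule:

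- Study Population requires participants to "report at least 2 current, active symptoms", meaning a score of 4 or less on any two SIBDQ items. It sets no threshold on the separate 0–10 symptom ratings.
- Study Outcomes, Symptoms: "Symptoms are measured using a numeric rating scale where participants report the severity of the symptom from 0=not present to 10=worst possible". Eleven single ratings follow: "Symptoms include abdominal pain, anxiety, bloating, constipation, depression, diarrhea, fatigue or tiredness, passing gas, sleepiness during the day, stress, and urgency". No composite GI score is described, neither its items nor whether it is a sum or a mean.
- Objectives, item 3, places response at post intervention. Participant Timeline and the primary analysis have two such visits, immediate and 3 months, and the responder definition does not choose between them.

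**The concern.** A percentage criterion asks for a smaller absolute change the lower the baseline. On a composite score, half a point suffices from a baseline of 1, while 2.5 points are needed from 5. At a baseline of 0 the percentage does not exist. Read as one composite, the *or* lets the GI criterion alone make a patient a responder.

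The candidate predictors include disease activity and fecal calprotectin, and the first half of aim 3 asks whether those same factors go with baseline symptoms. If a fall of 50% is easier to reach by chance in patients with mild GI symptoms, any marker of mild disease can separate responders from non-responders without any benefit of treatment. The comparison is confined to the intervention arm, so usual care cannot show how many would have responded by chance. The planned arm has 36 patients, and a few misclassified ones can change the result. The Discussion (Future Directions) foresees further research on predictors of response.

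**Working it through.** **The plan's own figure.** No responder rate and no power for the responder comparison are given. The only aim 3 figure is 80% power for a correlation of 0.45. With Fisher's z, n = 36 and two-sided alpha 0.05 (assumed): atanh(0.45) × √33 − 1.960 = 0.4847 × 5.745 − 1.960 = 0.825, and Φ(0.825) = 79.5%. That reproduces the figure, but for a correlation, not for a responder split.

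**Inputs from the documents.** Ratings 0–10 with 0 allowed; response = follow-up at or below half of baseline; no baseline minimum; six of the eleven ratings are GI symptoms (abdominal pain, bloating, constipation, diarrhea, passing gas, urgency).

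**Assumptions.** No true change; independent normal noise at each visit with SD 1.0 to 1.5; scores truncated to 0–10; 200,000 draws per setting. The documents give no SD. The score is undefined, so it was built in two ways: (a) noise placed directly on one continuous score; (b) the mean of six whole-number ratings, with the SD applying to each item and between-item error correlation of 0 or 0.5.

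**Share with a 50% fall, among patients with baseline above 0:**

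| True score | (a) One score | (b) Six-item mean, correlation 0 | (b) Six-item mean, correlation 0.5 |
|---|---|---|---|
| 1 | 37–45% | 12–15% | 28–33% |
| 2 | 19–30% | 2–6% | 13–22% |
| 5 | 1–7% | 0% | 0.2–3% |

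**Check by formula for (a).** Follow-up minus half of baseline has mean μ/2 and SD σ√1.25. At μ = 5, σ = 1.0: Φ(−2.5/1.118) = 1.3%. At σ = 1.5: Φ(−2.5/1.677) = 6.8%. Both agree with the table. At low μ the truncation matters, hence the simulation.

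**Baseline of exactly 0 at a true score of 1.** For (a), Φ(−1/σ) gives 15.9% to 25.2%. For (b) with independent errors, an item rounds to 0 with probability Φ(−0.5/σ), that is 0.3085 to 0.3695; to the sixth power this is 0.0009 to 0.0025, under 0.3%. With correlation 0.5 it is 5–7%.

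**Ceiling on the SIBDQ criterion.** The scale has ten items scored up to 7 ("Total score range: 10 to 70"). The highest eligible baseline is 2 × 4 + 8 × 7 = 64. From 63 or 64 the most a patient can gain is 7 or 6 points, so the 8-point criterion is out of reach and the GI criterion is the only route. A patient who also has a GI baseline of 0 cannot respond by either.

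**The case against.** Several points on the other side stand.

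- The size depends on how the score is built. A six-item mean with independent errors brings the chance rate at a true score of 1 down to 12–15%, and zero baselines almost vanish. But six symptoms rated together by one patient may well vary together, and the gradient from mild to severe remains under each construction tried. That the answer turns on an undefined score is a reason to define it.
- Nothing shows that low GI scores will be common. The clinic is a tertiary one, and Strengths and Limitations says its patients may be more refractory. Against that, recruitment aims for purposeful sampling on characteristics that include disease activity.
- The *or* could mean two alternative definitions, not one composite, and the GI criterion cites an earlier trial of the parent programme in irritable bowel syndrome that may define the score. The plan itself settles neither.
- The analysis is exploratory, and Sample Size concedes that only large effects or correlations are detectable.

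A reader might infer more than the text supports. It does not follow that patients with a GI baseline of 0 cannot be classified: only the GI criterion is undefined for them, and a SIBDQ gain of 8 still classifies them. Nor is it right that no time point is given; Objectives says post intervention, and what is missing is the choice between two visits. Nor can one say that patients with low GI scores will become responders by noise, only that they may.

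**Conclusion.** The point holds as a cheap improvement to the exploratory second half of aim 3. As written, the rule ties responder status to baseline GI severity through a score that the documents do not define, without an entry floor or a rule for a baseline of 0. With no true change, the chance of meeting the GI criterion is about 12–45% at a true score of 1 across both constructions, against 0–7% at 5. These figures rest on an assumed noise SD of 1.0 to 1.5 and, for the six-item mean, an error correlation of 0 to 0.5. Without a baseline distribution, the number of the 36 patients affected cannot be stated. The mixed models for quality of life and symptoms use baseline-adjusted continuous change and are not affected.

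**What to change.** In Statistical Analysis, Secondary Outcomes:

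1. Name the one follow-up visit at which response is assessed.
2. Define the GI symptom score as the mean of the six GI ratings already collected.
3. Report the SIBDQ and GI criteria separately, not joined by *or*.
4. As the main predictor analysis, relate each factor to change in SIBDQ and in the GI score as continuous outcomes adjusted for baseline, as the plan already does for its primary outcomes.
5. If a 50% rule is kept, apply it only above a prespecified minimum baseline, which also settles the case of a baseline of 0.
6. State that patients with baseline SIBDQ of 63 or 64 cannot gain 8 points, and report how many there are.

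The cost is a few sentences and a little more analysis, with no new data collection. Fewer patients will count as responders, and those at the SIBDQ ceiling lose the alternative route that the *or* gave them; the continuous analysis keeps them in.
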